11.2. Remote monitoring

Remote monitoring is a remote evaluation carried out by sponsor personnel or representatives (e.g., data management personnel, statisticians, or clinical monitors) at a location other than where the Principal Investigator or clinical investigation personnel is located. Remote monitoring processes can provide many of the capabilities of monitoring as well as additional capabilities.

In addition to monitoring visits at the Principal Investigator or clinical investigation personnel's location, remote monitoring of the data entered in the eCRF system could be used to achieve the following:

- Conduct activities such as: standard checks of range, consistency, and completeness of data and checks for unusual distribution of data, such as too little variance)
- Special attention will be given in case of frequent data anomalies or errors, protocol deviations or excessive dropouts.
- Augment monitoring at PI location by performing monitoring activities that can only be accomplished using centralized processes (e.g., statistical analyses to identify data trends not easily detected)
- Monitor data quality through routine review of submitted data in real-time to identify missing data, inconsistent data, data outliers, and potential protocol deviations that may be indicative of systemic and/or significant errors in data collection and reporting
- Verify source data remotely, provided that both source data and CRFs can be accessed remotely
- Conduct aggregate statistical analyses of study data to identify subject data that are outliers relative to others and to evaluate individual subject data for plausibility and completeness
- Conduct analyses of site characteristics, performance metrics (e.g., high screen failure rates, high frequency of eligibility deviations, and delays in reporting data), and clinical data to identify early on corrective actions needed for characteristics correlated with poor performance or noncompliance

11.3. Data retention

The Investigator file must be archived for a minimum period of 10 years after the final clinical investigation report has been signed.

12. Amendments to the Clinical Investigation Plan

No changes in the clinical investigation procedures shall be affected without mutual agreement between the principal investigator and the sponsor. The agreement of the changes must be documented by signing the corresponding clinical investigation plan amendments and registered in the Change Log.

All significant changes require notification to the EC. Substantial changes may require approval from the EC prior to implementation. (Example of significant change: Changes of inclusion criteria, end points or assessment methods)

13. Deviations from the Clinical Investigation Plan

Deviations to the Clinical Investigation Plan occurs when the activities during the clinical investigation do not comply with the EC approved investigation plan.

A minor deviation is defined as those that don't increase risk or decrease benefit or don't have a significant effect on the subject's rights, safety, or welfare; and/or on the integrity of the data. If a deviation increases risk or decreases benefit and/or; has a significant effect on the subject's rights, safety, or welfare and/or has a significant effect on the integrity of the data it is defined as a major deviation and the Investigator must inform the monitor immediately, and the Monitor will report and inform the Clinical Manager or designee immediately.

The investigator is not allowed to deviate from the Clinical Investigation Plan unless, under emergency circumstances or to protect the rights, safety, and welfare of the subject(s).

For the purposes of this investigation, any variance from the protocol is considered a deviation and is to be reported.

The Clinical investigation personnel will complete a deviation eCRF form for all data-related deviations and all deviations that are not related to the data (*for example, an untrained nurse performing study procedures*) are reported by the monitor in the Site Report – Periodic Monitoring and actions are addressed to the Investigator for completion.

If any deviations to the investigation plan are detected during the monitoring visit, the Monitor shall ensure the site reports all deviations in the eCRF or on the Deviation log in the Investigator File. Additionally, the monitor must report any deviation noted during the visit in the Periodic Monitoring Report.

Monitor will align with data management in each investigation, how data management will be informed about all deviations.

The following information about the deviation will be collected:

- Date the deviation took place.
- State what the deviation is related to.
- Does the deviation affect data integrity?
- Does the deviation affect the subject's safety?
- Clear and concise description of the event.
- Corrective action taken.

14. Device Accountability

All access to the investigational devices (Heylo $^{\text{M}}$) used in the clinical investigation is controlled by storage procedures and device accountability logs as described below. The investigational devices must only be used in this clinical investigation and only according to the CIP.

Sponsor keeps a device accountability log that states the physical location of all investigational devices.

The PI or an authorized designee keeps records documenting the receipt, use and return and disposal of the investigational devices, which includes:

- Date of receipt.
- Identification of each investigational device (batch no./serial no./unique code).
- The expire date, if applicable.
- The date(s) of use.
- Subject identification.
- The date on which the investigational device was returned/explanted from the subject, if applicable.
- The date of return unused, expired or malfunctioning investigational devices, if applicable.

15. Statement of compliance

The clinical investigation is conducted in accordance with:

- Ethical principles that have their origin in the Declaration of Helsinki, 1964, Last amended at the 59th WMA General Assembly, Brazil, October 2013.
- MDD 93/42/EEC as amended by Directive 2007/47/EC (commonly known as the Medical Device Directive).
- MDR (EU) 2017/745
- ISO 14155:2020 "Clinical Investigation of medical devices for human subjects Good clinical practices".
- Any applicable regional or national regulations will be specified in the country specific CIP.

15.1. Ethics committee and regulatory authorities

The Clinical investigation plan and/or other relevant documents are submitted to the appropriate EC. This clinical investigation will not begin until the required approval from the EC have been obtained. Any amendment to the protocol will be submitted to the same EC.

Sponsor will notify the relevant regulatory authority and EC concerned of the end of the clinical investigation.

15.2. Data protection

As part of the investigation Coloplast A/S, [name] ("Coloplast") will collect and process the personal information the subject provides for the investigation ("subject personal data"). This includes identification and contact information (which may be anonymised depending on the nature of the investigation) as well as information about product usage experience and your health. Coloplast will comply with the EU General Data Protection Regulation (GDPR) and the Danish act on data protection ("databeskyttelsesloven"), including in connection with transfer of data to third countries, cf. chapter V of GDPR, Coloplast will only process the subjects' personal data:

- 1. To conduct the investigation and carry out related research based on subject consent (primary use), cf. articles 6(1)(a) and 9(2)(a) of GDPR,
- 2. To comply with applicable legal obligations to e.g. ensure reliability and safety, cf. article 6(1)(c) in conjunction with article 9(1)(i) of GDPR, and
- 3. If separate consent is given for secondary use of subject personal data, cf. articles 6(1)(a) and 9(2)(a) of GDPR carry out research outside the clinical protocol to improve Coloplast's products and services, and for use in education.

Part of Coloplast's processing is carried out on third-party platforms (clinical trial databases) and certain third parties are assisting Coloplast in the processing (e.g. the investigator). Such cases will imply a transfer of your personal data to the third parties, but solely for the specified purposes and with the third parties acting on instruction from Coloplast. Data may be collected and processed across the Coloplast network, which may entail processing of personal data outside the European Economic Area. In such cases, an adequate level of protection will be ensured by the third parties being subject to the standard contractual clauses on data protection adopted by

the EU or to an EU-approved certification mechanism on data protection. For further information about this please the subject can always consult Coloplast's data protection officer (details below).

Subject personal data will be kept as long as required under applicable laws and regulations. The EU Medical Device Regulation obligates Coloplast to keep the data for a period of at least ten years after the investigation is completed, or, in the event that the device is subsequently placed on the market, at least ten years after the last device has been placed on the market. Subject personal data will be deleted at the end of the mandatory retention period.

If the subject has questions or queries regarding Coloplast's handling of personal information, the subject can always contact Coloplast's Data Protection Officer at Coloplast's handling of subject personal information may similarly be sent to the Data Protection Officer, and the subject is also entitled to file a complaint with the relevant supervisory authority, which in the case of Denmark is the Danish Data Protection Agency (www.datatilsynet.dk).

The subject can write to a subject can write to a subject can write to request:

- Access to personal data
- Correction of errors in personal data or to erase personal data
- Limit what can be done with personal data
- To receive personal data in machine-readable format (data portability).
- Withdrawal of consents the subject has given Coloplast to process personal data

15.3. Indemnity

All subjects are fully covered by Coloplast A/S insurance throughout the investigation.

15.4. Financial conditions

Coloplast A/S will compensate the Principal investigator involved in the clinical investigation for his time and resources spent on the investigation. All financial agreements with the Principal investigator involved in the clinical investigation will be specified in the sponsor investigator agreement.

The expenses include the salary to the Principal Investigator, the cost of external clinical support, study supplies, eCRF (Smart Trial), Investigator training meeting and travel expenses for nurses attending the Investigator meeting and patient expenses (including travel expenses). The Principal Investigator and study nurses have no financial interest in the investigation. The total budget for the investigation is expenses are paid on an ongoing basis.

Subjects will be paid fo	or their participation in the study, o	and they will receive the payment via bank transfer. to
	per visit 1 to visit 3, and	per follow-up call /after V1 and V2), in total
if the subject com	pletes the investigation. Payment	will be done after visit 3 unless subject terminates ear-
lier.		

16. Informed consent process

Written informed consent is obtained from all subjects participating in the investigation after thorough written and verbal information. The information is given by the investigator or his/her representative in the subjects' native non-technical language. Each subject will be fully informed about the aim of the investigation, procedures, potential risks, or inconveniences and/or expected benefits, all anticipated adverse device effects and then have a minimum of 24h before deciding on participation. The subjects will be informed that their participation is voluntary and that they may leave the investigation at any time, without this having any influence on their further treatment.

The informed consent signature form includes personally dated signatures of the subject and the PI or his/her representative responsible for conducting the informed consent process. A copy will be provided to the subject.

If new information is to be given during the investigation, sponsor will inform the investigators, and the new information is given to the subjects by the investigator. If new information becomes available that can significantly affect a subject's future health and medical care that information will be provided to the subject in written form. CM is responsible for writing the information and providing the approved Subject Information and Consent Form to investigators that will further provide it to the subjects. If applicable, all affected subjects shall be asked to confirm their continuing informed consent in writing.

This procedure also applies to informed consent obtained from a subject's legal representative. The procedure cannot waive the subjects' legal rights.

17. Subject compensation

17.1. Compensation in case of injury

Product liability and No-Fault Clinical Investigation Insurance covering the duration of the clinical investigation are in place, to enable compensation in the event of an injury to a participating subject, see section 15.3

17.2. Compensation for participating in the clinical investigation

Subjects will be compensated for their participating in the clinical investigation as described under Financial conditions 15.4.

18. Adverse events, adverse device effects and device deficiencies

18.1. Adverse events

An adverse event is any untoward medical occurrence, unintended disease or injury, or untoward clinical signs (including abnormal laboratory findings) in subjects, whether or not related to the investigational medical device(s) or the comparator(s), or the procedures involved. The adverse event shall be marked with the intensity mild, moderate or severe. This could include events such as headache or dizziness.

18.2. Adverse device effect

An adverse event, which is related to the use of the investigational medical device, is an adverse device effect, and should be marked as unlikely related, possible related, probable related or with causal relationship on the adverse event form.

The definition of an adverse device effect includes any event resulting from insufficiencies or inadequacies in the instruction for use, deployment, implantation, installation and operation, or any malfunction of the medical device, as well as any event resulting from use error or from intentional misuse of the device.

Table 5 lists anticipated adverse device effects that may occur.

Table 5: Anticipated adverse device effects and their likely incidence rates

ANTICIPATED ADE	INCIDENCE RATE
Peristomal skin irritation (incl. mechanical trauma)	< 10%
Allergic peristomal skin irritation (dermatitis)	< 1%

Temporary redness upon removal of the base plate is not considered an adverse device effect, however an abnormal development in intensity or duration should be considered as such.

18.3. Device deficiency

A device deficiency is the inadequacy of the investigational medical device or comparator with respect to its identity, quality, durability, reliability, usability, safety, or performance. This includes malfunctions, use errors and inadequacy in the information supplied by the manufacturer including labelling.

Example: Transmitter not able to charge.

18.4. Serious adverse events (SAE)

A serious adverse event is an adverse event that:

- Led to death.
- Led to a serious deterioration in the health of the subject, users or other persons as defined by one or more of the following:
 - 1) a life-threatening illness or injury, or
 - 2) a permanent impairment of a body structure or a body function including chronic diseases, or
 - 3) in-patient or prolonged hospitalization, or
 - 4) medical or surgical intervention to prevent life-threatening illness or injury or permanent impairment to a body structure or a body function.
- Led to foetal distress, foetal death, a congenital abnormality, or birth defect including physical or mental impairment.

This includes device deficiencies that might have led to a serious adverse event if:

- 1) Suitable action had not been taken, or
- 2) Intervention had not been made, or
- 3) Circumstances had been less fortunate.

These are handled under the serious adverse event reporting.

Planned hospitalization for a pre-existing condition, or a procedure required by the CIP, without serious deterioration in health, is not considered a serious adverse event.

18.4.1. Serious adverse device effect (SADE)

A serious adverse device effect is an adverse device effect that has resulted in any of the consequences characteristic of a serious adverse event.

18.4.2. Anticipated serious adverse device effect (ASADE)

Anticipated serious adverse device effect is any effect that by its nature, incidence, severity, or outcome has been previously identified in the risk analysis report.

18.4.3. Unanticipated serious adverse device effect (USADE)

An unanticipated serious adverse device effect is a serious adverse device effect which by its nature, incidence, severity, or outcome has not been identified in the current version of the risk analysis report.

18.5. Medical care of subjects

Principal investigator shall ensure that adequate medical care is provided, during and after participation in the clinical investigation, to a subject experiencing an adverse event. All ongoing ADEs, SAEs, SADEs and DDs that could have led to a SAE at subject termination will be followed according to the Risk Benefit analysis (see 8.2) and will be followed until a resolution is addressed for a period of 2 months after subject termination. An ongoing adverse event at subject termination visit is documented as the current status for the adverse event and will not be followed up.

The subjects shall be informed of any new significant findings occurring during the clinical investigation, including the need for additional medical care that can be required, and of the nature and possible cause of any adverse events experienced.

Principal investigator or delegate shall provide the subject with the necessary instructions on proper use, handling,

storage and return of the investigational device when it is used or operated by the subject.

18.6. Reporting and timelines

18.7. Investigator's reporting responsibilities

- PI must assess all (S)AE's that occurs during the investigation.
- All serious adverse events and serious adverse device effects must be reported to sponsor within 24 hours of the Clinical investigation personnel becoming aware of the event.
- A device deficiency that could have led to a serious adverse event but did not because suitable action
 was taken, intervention had been made or because of fortunate circumstances should be reported to
 sponsor within 24 hours of the clinical investigation personnel becoming aware of the event.
- New findings and/or updates in relation to already reported serious events should also be reported to sponsor within 24 hours of the clinical investigation personnel becoming aware of the event.
- Device deficiencies and all adverse device effects related to CE marked Coloplast investigational product and/or comparator must be reported to sponsor within 24 hours of becoming aware of the event.

When reporting the SAE, the relationship to the test material shall be described whether the event is considered

- Not related, the event has no temporal relationship with the use of the test material or the
 o procedures.
- Unlikely related, the relationship with the use of the test material seems not relevant and/or the event can be reasonably explained by another cause, but additional information may be obtained.
- Possible related, the relationship with the use of the test material is weak but cannot be ruled out completely. Alternative causes are also possible (e.g. an underlying or concurrent illness/ clinical condition or/and an effect of another device, drug, or treatment). Cases where relatedness cannot be assessed, or no information has been obtained should also be classified as possible.
- **Probable related**, the relationship with the use of the test material seems relevant and/or the event cannot reasonably be explained by another cause, but additional information may be obtained.
- **Definitely related/Causal relationship,** the event has a temporal relationship with the test material use/application or procedures.

and the intensity of the event should be considered, as such:

- Mild, the intensity of the event is mild with no further action or intervention
- Moderate, the intensity of the event will lead to an action or intervention to solve the event
- Severe, the intensity of the event will lead to follow up on the action or intervention, as the effect of the action or intervention may not decrease the symptoms.

All above events must be reported by use of the relevant adverse event/serious adverse event/device deficiency form.

Please report to: Coloplast A/S [name]

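### The relatedness levels in section 18.7 overlap because the top level asks only for timing, and section 18.2 treats *unlikely related* events as device effects, so the count and grading of device effects are ambiguous

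*Combined protocol and SAP*

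**What the plan says.** Section 18.7 gives a five-level relatedness scale, introduced for serious events: "When reporting the SAE, the relationship to the test material shall be described whether the event is considered". At the bottom, *Not related* means "the event has no temporal relationship with the use of the test material" or the procedures. At the top, *Definitely related/Causal relationship* means "the event has a temporal relationship with the test material use/application or procedures". The middle levels use other criteria. *Unlikely* covers a link that does not appear relevant and/or the case where "the event can be reasonably explained by another cause, but additional information may be obtained". *Possible* is a weak link that cannot be excluded, and it is also the default: "Cases where relatedness cannot be assessed, or no information has been obtained should also be classified as possible". *Probable* is a link that appears relevant and/or an event with no other reasonable explanation.

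Section 18.2 defines the device effect: "An adverse event, which is related to the use of the investigational medical device, is an adverse device effect". It goes on to say that such an event "should be marked as unlikely related, possible related, probable related or with causal relationship on the adverse event form". It does not define those four labels, and 18.7 is the only place in the document that does.

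**The concern.** A causality scale should be ordered, and each event should fit one level. Here the two end levels are defined by timing and the three middle levels by causal judgement. The top level, which should be the hardest to reach, asks for less than *Probable* does.

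Heylo is worn with the subject's own baseplate throughout an 8-week period (section 5.1), so timing separates very little. It is least useful for the effect of most interest. Section 8.2 names skin irritation and mechanical trauma as risks of ostomy products generally, and section 4.3 places the sensor layer under the subject's usual baseplate. Peristomal irritation in the Heylo period could come from either product, and only a causal criterion can tell them apart.

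Device-effect status matters in practice. Section 18.7 requires all adverse device effects to reach the sponsor within 24 hours. Section 18.5 follows ongoing device effects for 2 months after termination, whereas other ongoing non-serious adverse events are not followed. Sections 18.4.1 and 18.4.3 build the serious and unanticipated serious device-effect classes on the same status.

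**Working it through.** **1. The levels side by side.** Take an event that starts while Heylo is being worn and that another cause reasonably explains. The plan does not define a temporal relationship; I take it to include onset during use.

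| Level (18.7) | Criterion, in short | Does the event meet it? |
|---|---|---|
| Not related | no temporal relationship | No, because it began during use |
| Unlikely | link does not appear relevant and/or other cause explains it | Yes |
| Possible | weak link, not excluded; other causes possible | Arguable |
| Probable | link appears relevant and/or no other reasonable cause | No, if the link does not appear relevant |
| Definitely/Causal | temporal relationship | Yes |

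The event meets *Unlikely* and *Definitely* together, fails *Probable*, and is barred from *Not related* however clear the other cause is.

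**2. Section 18.2 against 18.7.** In 18.2 the event must be related to the device, and one permitted mark is *unlikely related*. In 18.7 that mark describes a link that does not appear relevant. An event can therefore be judged not relevantly linked and still be counted as a device effect.

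**3. What moves the total and what does not.** Under 18.2 all four levels from *Unlikely* to *Causal* are device effects. Moving an event among these four leaves the total unchanged and alters only the split. The total depends on where *Not related* ends and on whether *Unlikely* counts.

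**4. Illustrative size.** The plan states no overall device-effect rate to reproduce, and none of the inputs below comes from the documents. Let r be the true rate of device effects, b the background rate of adverse events in the Heylo period, and u the share of background events marked *Unlikely* or higher. Assuming independence:

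reported proportion = 1 − (1 − r)(1 − b·u)

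| r | b | u | Reported proportion |
|---|---|---|---|
| 5% | any | 0 | 5.0% |
| 5% | 5% | 0.5 | 1 − 0.95 × 0.975 = 7.4% |
| 5% | 10% | 0.5 | 1 − 0.95 × 0.95 = 9.8% |
| 5% | 10% | 1 | 1 − 0.95 × 0.90 = 14.5% |
| 5% | 20% | 1 | 1 − 0.95 × 0.80 = 24.0% |
| 8% | any | 0 | 8.0% |
| 8% | 10% | 0.5 | 1 − 0.92 × 0.95 = 12.6% |
| 8% | 20% | 1 | 1 − 0.92 × 0.80 = 26.4% |

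If all 144 planned subjects are taken as the denominator, the range for r = 8% runs from 144 × 0.080 = 11.5 to 144 × 0.264 = 38.0 subjects. The literal wording pushes u towards 1 for events during use. An assessor who relies on clinical judgement pulls it towards 0.

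**The case against.** Several points on the other side stand.

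- **Scope.** The five definitions are introduced for SAE reporting. Applying them to non-serious events is an inference from the shared labels. It is a reasonable one, since 18.7 also asks the investigator to assess every event, serious or not. Without it, the labels in 18.2 have no definition at all.
- **SAE duties.** Every SAE goes to the sponsor within 24 hours (18.7) and to the authorities within 7 calendar days at the latest (18.8), whatever its relatedness. The wording changes none of this.
- **Forced assignment.** A reader might infer that every event in the Heylo period must be graded *Definitely related*. The documents do not say so. The middle levels remain available, and the top level carries the label of a causal relationship. The defect is overlap and ambiguity.
- **Interpretability.** A reader might also infer that the device-effect rate is meaningless. It is not: each event's level is recorded, so device effects can be tabulated by level and recounted without *Unlikely*. This remedy is only partial, because the same event can properly be marked *Unlikely* or *Definitely*. The recount then depends on which definition the assessor followed.
- **Table 5.** It is tempting to set an inflated overall rate against the figure of under 10%. Table 5 gives incidences for two named skin effects (under 10% and under 1%), not for all device effects. An unrelated headache would not enter either row, and no test against Table 5 is planned.

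Broad capture of *unlikely related* events may also be a deliberate, cautious choice. If so, the plan should say so, and 18.2 should not describe those events as related.

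**Conclusion.** The point holds as a defect in the definitions. The levels in 18.7 are not mutually exclusive, the top level has a weaker criterion than *Probable*, and 18.2 and 18.7 disagree on what *unlikely related* means. The split by level is therefore unreliable, and the total of device effects is ambiguous and liable to inflation.

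The size cannot be fixed from the documents. Under the assumed inputs above, the total lies between the true rate and about three to five times it (26.4/8.0 = 3.3; 24.0/5.0 = 4.8). The upper end requires a 20% background rate with every background event marked *Unlikely* or higher. The conclusion also rests on reading 18.7 as the source of the labels in 18.2.

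The consequences are confined to safety classification. Adverse events are assessed on the safety population with descriptive summaries and/or listings (10.1 and 10.1.1), and success depends only on the primary or secondary endpoint (10.4).

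**What to change.** 1. Rewrite the levels in 18.7 so that each event fits only one. The causal level should require, beyond timing, a plausible link to the device and no other reasonable cause. *Not related* should also be available when another cause clearly explains the event.
2. State that the same definitions apply to the marks in 18.2.
3. Reconcile 18.2 with 18.7 on whether *unlikely related* events are device effects, and record the decision before database lock.
4. Tabulate device effects by relatedness level, with *Unlikely* in its own row, so that either total can be read off.

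The cost is a few lines in the two sections and matching help text in the eCRF. There is one further consequence. Device-effect status determines which non-serious events fall under the 24-hour reporting in 18.7 and the 2-month follow-up in 18.5. Settling the status of *unlikely related* events therefore changes who is reported and followed, and the sponsor must reconcile those sections at the same time. This review does not propose where that line should fall.

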5.8. Blinding

No blinding will be used in this investigation, except for the statistician who will be blinded until Data Base Lock.

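### The adverse event intensity grades in section 18.7 turn on what was done about the event, so some events are misgraded and one kind has no grade

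*Combined protocol and SAP*

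**What the plan says.** Section 18.1 sets the requirement: "The adverse event shall be marked with the intensity mild, moderate or severe". It does not say what the three words mean.

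The meanings are given in 18.7, in a list introduced by "When reporting the SAE, the relationship to the test material shall be described whether the event is considered". After the relatedness categories come the three intensity categories:

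- The lowest grade is given as "Mild, the intensity of the event is mild with no further action or intervention".
- The middle grade, Moderate, is assigned when somebody has to do something in order to resolve what happened.
- The highest grade is given as "Severe, the intensity of the event will lead to follow up on the action or intervention". The reason offered is that what was done might leave symptoms no better.

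No other section offers an intensity scale. On blinding, 5.8 states: "No blinding will be used in this investigation, except for the statistician who will be blinded until Data Base Lock". Section 6 adds that homecare nurses from the sponsor's service carry out the visits. Section 5.3 lists adverse events among the assessments, 10.1 summarises assessments by product where relevant, and 10.1.1 bases the adverse event assessment on the safety population.

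**The concern.** An intensity grade is meant to say how bad an event was for the subject. Here two of the three grades say how the event was handled and whether the handling worked. The third adds a handling condition to a definition that repeats the word being defined. Handling depends on the habits of the nurse, the wishes of the subject and the options available, as well as on symptoms.

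The trial has no safety endpoint and no safety test, so the descriptive adverse event data and the ongoing review in 18.9 are its safety evidence. If the grade mixes intensity with handling, a reader of that evidence cannot tell which of the two a Moderate or Severe event reflects. In an open-label cross-over there is a further possibility. Staff and subjects know which product is in use, and if they act more readily in one period, intensity may differ by product when symptoms do not.

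The placement adds a second problem. The definitions sit under the reporting of serious events, while 18.1 asks for a grade on all events. Table 5 in 18.2 names peristomal skin irritation as an anticipated effect. Where such an event is not serious, no scale clearly applies to it.

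**Working it through.** The plan states no figure on this point and none can be derived, so the check is a reading of the three definitions against each other. Take two events, one slight and one intense, and three ways each may be handled. Then apply 18.7 literally.

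| Event | No action | One action, solved, no follow-up | Action that needs follow-up because it may not work |
|---|---|---|---|
| Slight | Mild | Moderate | Severe |
| Intense | No grade fits | Moderate | Severe |

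Cell by cell:

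1. **Slight, no action.** Both parts of the Mild definition are met. The grade is right.
2. **Slight, one action.** Mild is ruled out because something was done. Moderate asks only that the event led to an action. The grade is higher than the symptoms warrant.
3. **Slight, action needing follow-up.** This meets the wording of Severe, which names no level of symptoms.
4. **Intense, no action.** Mild fails because the intensity is not mild. Moderate and Severe fail because there was no action. The event has no grade, although 18.1 requires one, and the site has to guess.
5. **Intense, one action.** Severe fails because there was no follow-up of the action. The grade is Moderate, the same as for the slight event in item 2.
6. **Intense, action needing follow-up.** The grade is Severe, which is right, but it is the same grade as for the slight event in item 3.

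Once any action is taken, the slight and intense rows are identical, so handling alone fixes the grade. Four of the six cells (items 2 to 5) give a grade that does not match the symptoms, or no grade. These are logical cases and not frequencies; the documents give no data on how often each would occur.

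For a possible difference between products, the inputs would be the share of events that lead to an action, and to follow-up of that action, in each period. The documents give neither, so no size can be computed.

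**The case against.** The best defence is that the definitions are not wholly about handling. Mild names mild intensity, and the other two begin from the intensity of the event and describe what it leads to. An experienced nurse may read the action as a sign of intensity and grade sensibly. The consequence is also small. No endpoint, test, pass/fail criterion, stopping rule or reporting timeline uses the grade. Seriousness has its own criteria in 18.4, and 18.7 sends serious events and device effects to the sponsor within 24 hours whatever their intensity. No intensity-by-product table is specified, and the adverse event form is not among the documents, so action and outcome may already be separate fields. All of this stands and limits the weight of the point. It does not supply an anchor for Moderate or Severe, or a grade for an intense event that prompts no action.

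Three stronger readings are tempting, and the documents do not support them.

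- A reader might infer that a very painful event left untreated is graded mild and so hidden. Mild also requires mild intensity, so such an event has no grade.
- A reader might infer that device effects still open at the last visit become Severe, because 18.5 states "All ongoing ADEs, SAEs, SADEs and DDs that could have led to a SAE at subject termination will be followed". That is follow-up of an event after termination. The Severe definition concerns follow-up of an action that may not work, and nothing says events are regraded at termination.
- A reader might infer that the same irritation will be graded higher on Heylo, because resizing the sensor layer is an extra option there. Actions exist in both periods: subjects use their own baseplate and bag throughout (5.1), and a change in the stoma product is recorded for each test period (5.3, 7.1). One more possible action does not show a higher rate of action, and any figure put on the difference would only restate assumed rates.

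**Conclusion.** The point holds as a defect in a stated rule. Section 18.1 requires a grade for every adverse event, and the only definitions, placed under serious event reporting, misplace some events and leave one kind without a grade. This follows from the wording and needs no assumption beyond a literal reading.

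A difference in grading by product is a possibility only. It requires that decisions to act differ between periods, which the open-label design allows but the documents do not show, in size or in direction.

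The reach is limited to the descriptive intensity data and whatever use the ongoing safety review makes of them. The efficacy conclusions, the classification of events as serious and the 24-hour reporting are unaffected. The change is worth making because it is cheap beforehand, and because a grade that has absorbed handling cannot later be separated from it unless the action was recorded as well.

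**What to change.** Before first enrolment, planned for October 2021 in 5.9:

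1. Replace the three definitions in 18.7 with grades based on symptoms and on interference with the subject's usual activities. For example, Mild: noticed, with no interference; Moderate: some interference; Severe: usual activities prevented.
2. State in 18.1 and 18.7 that the scale applies to all adverse events, serious or not.
3. Check that the adverse event form records action taken and outcome in fields separate from intensity, and add them if it does not. This keeps what the present definitions were trying to capture.

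The cost is a rewording of 18.1 and 18.7, possibly a change to the form, and a line in the nurse training. The drawback is that intensity would be less directly comparable with earlier sponsor studies if those used the action-based scale; the separate action field would recover part of that. The change concerns how events are recorded and alters nothing in how subjects are managed.
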